	Date Revised:	7/22/2017
	Study Number:	IF# 2087568 , GCO#17-04304

local anesthesia safely under ultrasound guidance in the interspace between the popliteal artery and capsule of the knee.

There have been no studies till date comparing the efficacy between IPACK block and PAI.

3)Setting of the Human Research

Prospective triple blinded randomized control trial undergoing total knee arthroplasty surgeries. The research study will take place at Mount Sinai West hospital and Mount Sinai St. Luke's hospitals. The site PI is [name], MPH.

4)Resources Available to Conduct the Human Research

For n=200, the feasibility of recruitment is manageable. Recruitment will be done through a coordination of the operating schedule and the surgeon's office. Patients presenting for preoperative visits at the preoperative joint clinic will be approached. Patients routinely are seen by anesthesiologists at the pre operative testing clinic as part of pre operative anesthetic evaluation. Patients will be approached by research personnel and details of the study will be explained. The consent will be obtained in the pre operative testing clinic after all questions are thoroughly answered. After confirmation on the operating schedule, patients will be provided detailed instructions the day before surgery. The staff members on this protocol are all employees of Mount Sinai and will either be a resident or attending physicians that are included on the IRB protocol. There are two primary members of the research personnel:

a)[name], MPH – Roles for [name] in this study include serving as primary investigator responsible for study design and planning, data collection, subject recruitment, manuscript writing and preparation, data analysis, safety monitoring, and responding to adverse events and/or complications. He is certified in PPHS/IRB protocols, all Citi/IRB required training in human subject protection, and has prior clinical research experience. He is also a board certified anesthesiologist and assistant professor of anesthesiology with the Icahn School of Medicine and the Mount Sinai Health System.

 Mount Sinai	Protocol Name:	COMPARISON BETWEEN IPACK BLOCK AND PERIARTICULAR INFILTRATION IN TOTAL KNEE ARTHROPLASTY - A RANDOMISED CONTROLLED TRIAL
	Principal Investigator:	[name] [name].
	Primary Contact Name/Contact Info:	[name] MD. [REDACTED]
	Date Revised:	7/22/2017
	Study Number:	IF# 2087568 , GCO#17-04304

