b) [name] MD – Roles for [name] include serving as primary research coordinator involved in data collection, subject recruitment, manuscript writing and preparation, data analysis, safety monitoring, and responding to adverse events and/or complications. She has completed all of her required CITI training to be IRB certified and has experience in clinical research. In addition she has been a resident physician in anesthesiology with the Icahn School of Medicine in good standing for the previous three years going on her fourth.

There are institutional processes to ensure that all persons assisting with the protocol will be well informed. The research personnel will conduct regular meetings and department email updates to review the results and safety data of the study. The research personnel will initiate the formation of a safety monitoring board for adverse effects, complications, or complaints from patient subjects.

5) Study Design

Prospective triple blinded randomized control trial. Recruitment will be done through a coordination of the operating schedule and the surgeon's office. Patients presenting for preoperative visits at the preoperative joint clinic will be approached. Patients routinely are seen by anesthesiologists at the pre operative testing clinic as part of pre operative anesthetic evaluation. Patients who meet the inclusion criteria will be approached by research personnel and details of the study will be explained. The consent will be obtained in the pre operative testing clinic after all questions are thoroughly answered. The team will finalize participation and ask the subject to sign study consent forms. All patients will be provided with copies of the IRB protocol and consent if they wish to have it. Copy of the consent form will be sent in a secured email to the potential subject. The email will be secured by entering in [SECURE] in the e-mail subject line. Once recruited blinding assessments will be done by the study team.

Patients will be assigned randomly using a computer- generated table of numbers to either IPACK block (IPACK group) or Periarticular infiltration (PAI group). Block team will perform all blocks. Resident anesthesiologist will know the group allocation but will not be involved in the study. Patients assigned to IPACK block group will receive 20cc 0.25% bupivacaine under USG guidance on the side of

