 Mount Sinai	Protocol Name:	COMPARISON BETWEEN IPACK BLOCK AND PERIARTICULAR INFILTRATION IN TOTAL KNEE ARTHROPLASTY - A RANDOMISED CONTROLLED TRIAL
	Principal Investigator:	[name] [name].
	Primary Contact Name/Contact Info:	[name] MD. [REDACTED]
	Date Revised:	7/22/2017
	Study Number:	IF# 2087568 , GCO#17-04304

surgery. At the conclusion of the surgery prior to skin closure, all patients in the PAI group will receive 100cc of joint cocktail infiltrated by the surgeon. Patients in both groups will receive a post operative adductor canal catheter in the PACU, with Bupivacaine 0.1% 8-12 cc/hr with demand dose of 3-5 cc q20 min. Otherwise, the patient, surgeon, and anesthesiologist in the case will be blinded.

a) Recruitment methods: Patients will be recruited and consented in pre operative testing/Joint clinic.

b) Inclusion and Exclusion Criteria

Inclusion criteria: ASA (American Society of Anesthesiology) class I-IV, age 18-75.

Exclusion criteria: ASA class V, morbid obesity, patient refusal, patients with chronic pain or on pain medications, allergy to LA, patients receiving any additional regional techniques, coagulopathy, patients receiving systemic anticoagulation, local infection, and procedures anticipated to last more than 5 hours.

c) Number of Subjects

We intend to recruit 200 patients.

Based on a confidence level of 99% with a Z score of 2.58, standard deviation of .5 and a confidence interval of 10% our sample size should be 166. For ease of statistical calculations we rounded up to 200 patients. Based on previous literature pertaining to local articular infiltration in total knee arthroplasty and postoperative femoral nerve block, we found studies included anywhere from 40 to 100 patients. We intend to use a higher sample size to see any statistical significance.

$$Z^2 * (p) * (1-p)$$

ss = _____

$$c^2$$

Where:

 Mount Sinai	Protocol Name:	COMPARISON BETWEEN IPACK BLOCK AND PERIARTICULAR INFILTRATION IN TOTAL KNEE ARTHROPLASTY - A RANDOMISED CONTROLLED TRIAL
	Principal Investigator:	[name] [name].
	Primary Contact Name/Contact Info:	[name] MD. [REDACTED]
	Date Revised:	7/22/2017
	Study Number:	IF# 2087568 , GCO#17-04304

Z = Z value (2.58 for 99% confidence level)

p = percentage picking a choice, expressed as decimal (.5 used for sample size needed)

c = confidence interval, expressed as decimal (e.g., .01=±1)

Sample size= $[(2.58^2)(.5)(.5)]/(.1^2)=166$ subjects

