For effect size, we expect a Cos d medium effect of 0.5. The estimate for sample sizes was obtained by using the first set of pain scores obtained in the PACU. A previous study of 45 patients undergoing knee arthroplasty treated with a femoral nerve block reported a mean visual analog scale score of 3.6 (SD 1.1) upon movement, at 24 h (Singelyn et al. 1998). In an earlier study on total knee arthroplasties (Axelsson et al. 2005), the mean morphine consumption over 48 hours postoperatively was 64.6 (SD 36.3) mg in the placebo group.

The aim of this study was to investigate whether the IPACK technique could reduce the morphine consumption. The Mann-Whitney U test will be used for the analysis of the primary endpoint (morphine consumption). Mann-Whitney U test will be used to assess pain scores and the Bonferroni-Holm method was used to correct for multiple measures. Hospital stay, time to fulfill discharge criteria, knee function scores, and patient satisfaction scores will be analyzed using the Mann-Whitney U test. Dichotomous data will be analyzed using the chi-squared test or Fisher's exact test, as appropriate. Values of p < 0.05 were considered to be statistically significant.

d) Study Timelines

2017-2018 and subsequent data analysis. The subject's participation will be from time of enrollment in the pre-operative period until first 24 hours after surgery. Estimated date of enrollment completion will be when 200 eligible subjects are enrolled in final data analysis. Estimate date for study completion will be June 2018.

 Mount Sinai	Protocol Name:	COMPARISON BETWEEN IPACK BLOCK AND PERIARTICULAR INFILTRATION IN TOTAL KNEE ARTHROPLASTY - A RANDOMISED CONTROLLED TRIAL
	Principal Investigator:	[name] [name].
	Primary Contact Name/Contact Info:	[name] MD. [REDACTED]
	Date Revised:	7/22/2017
	Study Number:	IF# 2087568 , GCO#17-04304

e) Endpoints

The primary endpoints will be the amount of opioid consumption (in mg IV morphine equivalents) postoperatively up to 24 hours after the surgery.

f) Procedures Involved in the Human Research

Prospective randomized controlled trial and data analysis only. IPACK block and PAI. Intraoperative care of the patient will be provided by an anesthesia team member who is a part of the Mount Sinai System. The anesthesia provider will not be aware of the randomization of the patient. Standard post-operative orders will be written for patients during their time in the PACU.

g) Specimen Banking

N/A

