h) Data Management and Confidentiality

Data collected in excel file to be de-identified after initial collection. Excel file be subsequently encrypted and shared only between the above listed investigators via secure Mt. Sinai (chpnet) electronic mail. The information included in the data will be medical record number, age, gender, ASA class, type of surgery, pain score assessments, and time to first narcotic, total narcotic use and satisfaction/pain scores during the first 24 hours after surgery. Pain scores on arrival and discharge from PACU, PACU length of stay, location of pain, and ambulation distance with assistance on POD 1 as assessed by PT and activities of daily living (ADL's) on POD 1 as assessed by OT will be other data collected.

Only the research personnel will have access to the data. The data will be stored as a hard copy files and on a secure spreadsheet. The research personnel is responsible for the receipt of the data. The PI will keep the hard copies secure and any electronic data will be encrypted. No personal identifiers will be used. The data will undergo statistical analysis

 Mount Sinai	Protocol Name:	COMPARISON BETWEEN IPACK BLOCK AND PERIARTICULAR INFILTRATION IN TOTAL KNEE ARTHROPLASTY - A RANDOMISED CONTROLLED TRIAL
	Principal Investigator:	[name] [name].
	Primary Contact Name/Contact Info:	[name] MD. [REDACTED]
	Date Revised:	7/22/2017
	Study Number:	IF# 2087568 , GCO#17-04304

i) Provisions to Monitor the Data to Ensure the Safety of Subjects

Part I: Elements of Data and Safety Monitoring Plan

MSSM Principal Monitor:

Last Name: [name]

First Name: [name]

Academic Title: Attending Physician, Assistant Professor

Department: Anesthesiology

Mailing Address: Mount Sinai West [name]

[contact]

Fax:

E-mail: [contact]

MSSM Additional Monitor:

Last Name: [name]

First Name: [name]

Academic Title: Research Personnel, Physician

Department: Anesthesiology

Mailing Address: Mount Sinai West [name]

[contact]

Fax:

E-mail: [contact]

The principal monitor is a board certified anesthesiologist thus minimizing the risk to the subjects and further optimizing their health and wellbeing. Adverse events will be monitored as a standard of care everyone receives regardless of participation in the study. The safety and data information will be reviewed on a daily basis until the desired sample size is achieved. All temporary and/or permanent suspensions will be reported.

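### The primary Mann-Whitney test is valid but leaves age, gender and ASA class unused; prespecifying a covariate-adjusted rank analysis is a cheap improvement of uncertain, probably modest, size

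*Combined protocol and SAP*

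**What the plan says.** Section 5(e) defines the endpoint: "The primary endpoints will be the amount of opioid consumption (in mg IV morphine equivalents) postoperatively up to 24 hours after the surgery". The analysis text sits in section 5(c): "The Mann-Whitney U test will be used for the analysis of the primary endpoint (morphine consumption"). The threshold is given as "Values of p < 0.05 were considered to be statistically significant", with no statement of one- or two-sided testing.

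No covariate, stratification factor, adjusted model or adjusted sensitivity analysis appears anywhere in the document.

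Section 5(h) lists what will be recorded: "The information included in the data will be medical record number, age, gender, ASA class, type of surgery, pain score assessments", followed by further outcome items. Age, gender and ASA class are fixed before treatment. Hospital is not on the list, although sections 3 and 15 name two hospitals. Section 5(b) admits ASA classes I to IV and ages 18 to 75.

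On allocation, section 5 says only "Patients will be assigned randomly using a computer- generated table of numbers". It states neither a ratio nor any stratification.

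**The concern.** The eligible population is broad in age and ASA class. If postoperative opioid use varies with these characteristics, an unadjusted two-group test leaves that variation in the error term. Adjusting for variables fixed before randomisation is a standard way to recover it, and three such variables will be in the dataset anyway.

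Two things are at stake. One is some power, mainly if the true difference between two active techniques is smaller than the plan assumes. The other is prespecification. If an imbalance in ASA class or age turns up, the plan has no agreed response, and an adjustment added after unblinding would look chosen to suit the data.

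**Working it through.** **The plan's own figure.** Section 5(c) computes 2.58² × 0.5 × 0.5 / 0.1² = 166.41, stated as 166 and rounded up to 200. It reproduces. It is a precision formula for one proportion and contains no group difference, power or Mann-Whitney test, so covariate adjustment does not alter it. No target power is stated; the text says only "We intend to use a higher sample size to see any statistical significance". Power therefore has to be worked out separately.

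**Inputs from the documents.** Total N = 200 and standardised difference d = 0.5, both in section 5(c); significance level 0.05.

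**Assumptions.** 1:1 allocation (100 per arm), two-sided testing, no dropout, R² between 0 and 20%, and d = 0.3 as a smaller alternative effect. The Mann-Whitney test is given its large-sample efficiency for normal data, 3/π = 0.955.

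**Formulas.**
- Equivalent sample size = 200 / (1 − R²).
- Reduction in standard error = 1 − √(1 − R²).
- Power = Φ( d × √(0.955 × 100 / 2) / √(1 − R²) − 1.96 ).

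At d = 0.5 and R² = 0: √47.75 = 6.910; 0.5 × 6.910 = 3.455; 3.455 − 1.96 = 1.495; Φ(1.495) = 93.3%.

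At d = 0.5 and R² = 10%: 3.455 / 0.9487 = 3.642; 3.642 − 1.96 = 1.682; Φ(1.682) = 95.4%.

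| R² (assumed) | 200 patients act like | Reduction in SE | Power, d = 0.5 | Power, d = 0.3 |
|---|---|---|---|---|
| 0 (same as unadjusted) | 200 | 0 | 93.3% | 54.5% |
| 5% | 211 | 2.5% | 94.4% | 56.6% |
| 10% | 222 | 5.1% | 95.4% | 58.9% |
| 20% | 250 | 10.6% | 97.1% | 64.0% |

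The gain over the unadjusted test is about 1 to 4 points at d = 0.5 and about 2 to 10 points at d = 0.3.

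**Check by simulation.** The formula treats adjustment as free, so it was checked with 3,000 simulated trials per cell, 100 patients per arm. The outcome was lognormal with coefficient of variation 36.3/64.6, the cited morphine figures in section 5(c). Those cover 48 hours in a placebo group and were used only for shape. The rank ANCOVA carried one prognostic and three uninformative covariates.

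| R² | d = 0.5: Mann-Whitney | d = 0.5: rank ANCOVA | d = 0.3: Mann-Whitney | d = 0.3: rank ANCOVA |
|---|---|---|---|---|
| 0 | 93.3% | 92.7% | 55.1% | 53.6% |
| 5% | 93.2% | 93.6% | 53.2% | 54.2% |
| 10% | 93.1% | 94.8% | 52.1% | 55.9% |
| 20% | 92.5% | 96.5% | 56.3% | 63.7% |

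With no true difference, both methods rejected in 4.4% to 5.3% of trials. The simulated gains agree in pattern with the formula and are a little smaller at d = 0.3. With useless covariates the loss is about half a point at d = 0.5. At d = 0.3 it is about 1.5 points, but each of those two power estimates has a simulation standard error of about 0.9 point (√(0.55 × 0.45 / 3000)).

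**The case against.** The strongest reply is that nothing here is wrong. An unadjusted Mann-Whitney test is valid in a randomised trial, and with no stated stratification factor the design does not oblige anyone to adjust. At the only effect size the plan gives, power is already about 93%. The exclusion of people with chronic pain or existing analgesic use may also remove some of the variation that covariates would explain. All of this stands, and it is why the point is an improvement and not a defect.

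The 93% needs one qualification. Section 5(c) ties the sample-size estimate to pain scores in the PACU, and its morphine figure covers 48 hours in a placebo group. Neither grounds d = 0.5 in 24-hour opioid use. Both arms receive an active technique plus an adductor canal catheter, so a smaller difference is plausible, and there the gain is larger.

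A reader might infer more than the documents support:
- **That precision is certainly thrown away.** The documents give no R². At zero nothing is gained and a little power is lost.
- **That hospital is available for adjustment at no cost.** Two hospitals take part, but site is not a listed data item and the spreadsheet is to be stripped of identifiers after collection.
- **That possible imbalance between hospitals undermines the result.** Chance imbalance is already covered by the test's type I error, and the documents give no hospital difference in opioid use. The absence of stratification is itself only inferred from silence.
- **That any adjusted model brings the same gain.** The 200/(1 − R²) reasoning comes from the linear model and carries over approximately to ranks. It does not carry over to a proportional-odds model, where adjustment changes the quantity being estimated.

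**Conclusion.** The point holds as a cheap improvement. The planned primary test is valid and does not use three baseline variables already in the dataset, so some precision may be lost. At the plan's d = 0.5, adjustment moves power from about 93% to between 93% and 97% for R² of 0 to 20%. At d = 0.3, it moves power from 54.5% to at most 64.0%. These figures rest on 1:1 allocation, two-sided testing, full follow-up of 200 patients and an assumed R². The documents do not support calling the unadjusted test biased or erroneous.

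**What to change.** Before unblinding, replace the primary-analysis sentence in section 5(c) with one named method: a rank-based ANCOVA. Rank 24-hour opioid consumption across all patients, then regress the ranks on arm, age, gender and ASA class. State how age is coded and the rule for pooling sparse ASA classes. Keep the unadjusted Mann-Whitney test as a sensitivity analysis, and report an effect estimate with a confidence interval.

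Include hospital only if a site field is added to the section 5(h) list before the file is de-identified.

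The cost is a few lines of text, one extra data field if hospital is used, and a small loss of power (about half a point at the plan's effect size) if the covariates turn out not to be prognostic. No extra patients are needed.

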Local infiltrative analgesia administered by the surgeon around the joint capsule has been an emerging adjunct to multimodal analgesia advocated by surgeons claiming improved rehabilitation by reducing venous stasis and maximizing motor strength. Periarticular analgesia (PAI) primarily targets the mechanoreceptors and the free nerve endings in the intra articular area.

 Mount Sinai	Protocol Name:	COMPARISON BETWEEN IPACK BLOCK AND PERIARTICULAR INFILTRATION IN TOTAL KNEE ARTHROPLASTY - A RANDOMISED CONTROLLED TRIAL
	Principal Investigator:	[name] [name].
	Primary Contact Name/Contact Info:	[name] MD. [REDACTED]
	Date Revised:	7/22/2017
	Study Number:	IF# 2087568 , GCO#17-04304

IPACK block is a novel technique gaining popularity where one injects local anesthesia safely under ultrasound guidance in the interspace between the popliteal artery and capsule of the knee. It primarily targets genicular nerves innervating the knee joint. It does not affect the sciatic nerve hence motor blockade is avoided promising enhanced recovery.

There have been no studies till date comparing the efficacy between IPACK block and PAI.

The purpose of our study is to evaluate the difference in quality of analgesia between efficacy of IPACK block and PAI performed by surgeon as measured by patient's opioid consumption and pain scores.

1) Objectives

Research Question: Does IPACK block provide superior analgesia in comparison with surgeon performed periarticular infiltrate (PAI) in TKA patients?

Primary outcome: The amount of opioid consumption (in mg IV morphine equivalents) postoperatively during the first 24 hours after the procedure. VAS pain scores on arrival and departure from PACU.

Secondary outcome:

The degree of postoperative pain in terms of VAS scores from arrival to the floors to the first 24 hours after surgery.

Time to first dose of narcotic administration, PACU length of stay, location of pain, ambulation distance with assistance on POD 1 as assessed by PT and activities of daily living(ADL's) on POD 1 as assessed by OT.

2) Background

See above. There have been several studies regarding efficacy of peri-articular infiltration. IPACK block is a novel technique gaining popularity where one injects

 Mount Sinai	Protocol Name:	COMPARISON BETWEEN IPACK BLOCK AND PERIARTICULAR INFILTRATION IN TOTAL KNEE ARTHROPLASTY - A RANDOMISED CONTROLLED TRIAL
	Principal Investigator:	[name] [name].
	Primary Contact Name/Contact Info:	[name] MD. [REDACTED]

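### Do the mismatched outcome names in Section 5c, and the lack of a rule for opioid-free patients, leave the secondary analyses undefined?

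*Combined protocol and SAP*

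**What the plan says.** Section 1 (Objectives) declares six secondary outcomes. The first is VAS pain from arrival on the floor to 24 hours. The next four are "Time to first dose of narcotic administration, PACU length of stay, location of pain, ambulation distance with assistance on POD 1", and the sixth is ADLs on POD 1 as assessed by occupational therapy.

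Section 5e lists opioid consumption alone: "The primary endpoints will be the amount of opioid consumption (in mg IV morphine equivalents) postoperatively up to 24 hours after the surgery".

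The statistical text in Section 5c names Mann-Whitney for morphine consumption. It then gives three further rules:

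- pain scores: "Mann-Whitney U test will be used to assess pain scores and the Bonferroni-Holm method was used to correct for multiple measures";
- four other outcomes: "Hospital stay, time to fulfill discharge criteria, knee function scores, and patient satisfaction scores will be analyzed using the Mann-Whitney U test";
- a class of data, with no outcome named: "Dichotomous data will be analyzed using the chi-squared test or Fisher's exact test, as appropriate".

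Section 5h lists the data to be held, including "time to first narcotic, total narcotic use and satisfaction/pain scores during the first 24 hours after surgery" and "Pain scores on arrival and discharge from PACU, PACU length of stay, location of pain, and ambulation distance with assistance on POD 1", together with ADLs and the medical record number.

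Section 5d sets the follow-up: "participation will be from time of enrollment in the pre-operative period until first 24 hours after surgery".

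**The concern.** Read literally, Section 5c describes the secondary analysis of a somewhat different trial. It tests hospital stay, time to meeting discharge criteria and knee function, which this trial neither declares nor lists for collection. A hospital stay or discharge time beyond 24 hours would also fall outside the stated participation. Meanwhile most of the declared secondaries have no test attached to their name, so the method could in principle be picked after the data are seen.

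Time to first narcotic raises a sharper question. A patient with no opioid by 24 hours has no observed time. Leaving such patients out would condition on something that happens after randomisation, and could hide an effect that works by sparing patients opioids altogether.

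**Working it through.** **Step 1. Match the lists.** The plan gives no figure on this point, so the first check is a side-by-side reading.

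| Outcome | Declared (1 or 5e) | In 5h data list | Test in 5c |
|---|---|---|---|
| Opioid use to 24 h | yes (primary) | yes | Mann-Whitney, by name |
| VAS pain, floor to 24 h | yes | yes | Mann-Whitney, by name |
| Time to first narcotic | yes | yes | none by name |
| PACU stay | yes | yes | none by name |
| Location of pain | yes | yes | chi-squared/Fisher if dichotomous |
| Ambulation distance, POD 1 | yes | yes | none by name |
| ADLs, POD 1 | yes | yes | chi-squared/Fisher if dichotomous |
| Satisfaction | no | yes | Mann-Whitney, by name |
| Hospital stay | no | no | Mann-Whitney, by name |
| Time to discharge criteria | no | no | Mann-Whitney, by name |
| Knee function | no | no | Mann-Whitney, by name |

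Three of the four outcomes in the quoted sentence are unmatched. Among the six declared secondaries, 6 - 1 = 5 have no test by name. Crediting pain location to the dichotomous-data rule leaves 4, and crediting ADLs as well leaves 3. The documents give no scale for either, so the honest count is three to five.

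**Step 2. Apply the default in the text.** Every outcome that 5c names gets Mann-Whitney, and dichotomous data get chi-squared or Fisher. Extending this puts PACU stay, ambulation distance and scored ADLs under Mann-Whitney, and pain location under chi-squared or Fisher. A fresh specification would choose the same tests, so nothing changes for these outcomes.

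**Step 3. Time to first narcotic.** The documents give no opioid-free share, time distribution or effect for this outcome, so every input here is assumed. The simulations used 100 per arm (200 split equally), two-sided 0.05, 24 h follow-up and 10,000 trials per scenario. Power was found for three analyses: Mann-Whitney among opioid users only, Mann-Whitney with opioid-free patients tied at 24 h, and log-rank with censoring at 24 h.

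| Assumed pattern | Opioid-free | Users only | Tied Mann-Whitney | Log-rank |
|---|---|---|---|---|
| Hazard ratio 0.65 throughout | PAI 5% | 0.396 | 0.739 | 0.826 |
| | PAI 10% | 0.259 | 0.723 | 0.792 |
| | PAI 20% | 0.153 | 0.693 | 0.740 |
| | PAI 30% | 0.101 | 0.640 | 0.676 |
| Effect on opioid-free share only | 5% vs 15% | 0.050 | 0.239 | 0.481 |
| | 10% vs 25% | 0.050 | 0.456 | 0.709 |
| | 20% vs 35% | 0.050 | 0.460 | 0.604 |
| Hazard ratio 0.5, fading to 1.0 at 6 h | PAI 10% | 0.655 | 0.663 | 0.433 |
| same, at 8 h | PAI 10% | 0.775 | 0.800 | 0.598 |
| same, at 12 h | PAI 10% | 0.862 | 0.925 | 0.836 |
| No effect | 10% | 0.051 | 0.050 | 0.051 |

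- *Users only against tied Mann-Whitney.* In the first two patterns the loss runs from 0.239 - 0.050 = 19 points to 0.693 - 0.153 = 54 points. With a fading effect it is about 0 to 10 points over PAI shares of 5% to 20%. In the share-only pattern the 5% power of users-only is built in, because users' times are the same in both arms.
- *Log-rank against tied Mann-Whitney.* The difference runs from 0.709 - 0.456 = +25 points to 0.433 - 0.663 = -23 points.
- *Few opioid-free patients.* In smaller runs (3,000 trials), shares of 1% vs 3% with no other effect gave about 6%, 6% and 8%. A hazard ratio of 0.65 with 1% opioid-free on PAI still gave 60%, 74% and 84%, but that implies 0.01^0.65 = 5% opioid-free on IPACK.

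**The case for a change.** The best case for a change is that three outcomes are unmatched on any literal reading, that time to first narcotic, PACU stay and ambulation distance lack a named test however pain location and ADLs are scored, and that repair needs only wording. Opioid-free patients are also plausible: Section 5 gives everyone an adductor canal catheter, and Section 5b excludes patients with chronic pain or on pain medications. Even with Mann-Whitney as the default, nothing says whether these patients are ranked last or left out.

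The mismatch and the missing rule both stand as facts. Their consequences are weaker.

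- Hospital stay and PACU stay, and knee function and the physical and occupational therapy assessments, are plausible pairs of terms. Hospital stay could also be taken from the chart through the medical record number.
- The freedom to pick a test afterwards is small, because the text uses one test for everything it names apart from the dichotomous class.
- The Holm clause sits in the pain-score sentence, and pain scores are its natural scope.
- The power losses arise under an analysis the plan does not propose, with shares and effects that come from outside the documents.

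**Conclusion.** No change follows. The unmatched terms are loose drafting, and the missing test names are a gap that the plan's own default fills. The primary endpoint is untouched, and PACU stay, ambulation distance, ADLs and pain location would be analysed the same way either way.

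For time to first narcotic, a competent analyst would keep opioid-free patients in the comparison, ranked as longest or censored at 24 h. Leaving them out could cost up to 54 points of power in the assumed scenarios, but the plan does not call for that. Between the two sound methods the difference runs from +25 to -23 points according to an effect pattern the documents do not give, so there is no clearly better method to substitute.

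This conclusion rests on two assumptions: that the default in Section 5c is carried to the declared secondaries, and that opioid-free patients are not dropped. If a report did drop them, the result for that one secondary outcome should be read with caution.

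### No preoperative VAS is specified, so the VAS outcomes cannot be adjusted for baseline pain: a modest loss of efficiency and description, not a bias

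*Combined protocol and SAP*

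**What the plan says.** **Outcomes.** Section 1 (Objectives) puts "VAS pain scores on arrival and departure from PACU" under the primary outcome, next to opioid consumption. Its first secondary outcome is "The degree of postoperative pain in terms of VAS scores from arrival to the floors to the first 24 hours after surgery". Section 5e (Endpoints) names opioid use alone: "The primary endpoints will be the amount of opioid consumption (in mg IV morphine equivalents) postoperatively up to 24 hours after the surgery".

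**Data fields.** Section 5h opens with "The information included in the data will be medical record number, age, gender, ASA class, type of surgery, pain score assessments". It goes on to "total narcotic use and satisfaction/pain scores during the first 24 hours after surgery" and then "Pain scores on arrival and discharge from PACU, PACU length of stay, location of pain". The last two are dated and postoperative. The pain item in the first has no date.

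**Analysis.** The statistical text in section 5c (Number of Subjects) says: "Mann-Whitney U test will be used to assess pain scores", with a Bonferroni-Holm correction for multiple measures. It plans no covariate adjustment and mentions no baseline score.

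**Preoperative contact.** Section 5 (Study Design) says: "The consent will be obtained in the pre operative testing clinic after all questions are thoroughly answered". Section 5d (Study Timelines) starts participation at preoperative enrolment.

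**The concern.** A VAS score is a personal rating, and patients differ in how they use the scale. A score from the same patient before surgery is an obvious candidate covariate. Where it correlates with the later scores, it removes part of the between-patient variation from the comparison of arms. Without it, that variation stays in the error term, and the baseline table cannot show whether the arms started with similar pain.

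VAS is not peripheral in this trial. It appears under both outcome headings in section 1, and section 5c says the sample-size estimate drew on the first PACU pain scores. The study team already meets every patient at a preoperative clinic visit. A standardised preoperative score cannot be taken once surgery is over, so a later change to the analysis plan alone could not supply it.

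**Working it through.** **1. Is a baseline score specified?**

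| Pain score | Where | Timing |
|---|---|---|
| VAS at PACU arrival and departure | Sections 1 and 5h | Postoperative |
| VAS from floor arrival to 24 h | Section 1 | Postoperative |
| Pain scores over the first 24 h | Section 5h | Postoperative |
| Pain item in the first list of fields | Section 5h | Not stated |

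Nothing assigns the undated item to the clinic visit, and no analysis uses a baseline. The accurate statement is that none is specified.

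**2. The plan's own sample-size figure.** Section 5c uses Z²·p·(1−p)/c² = 2.58² × 0.5 × 0.5 / 0.1² = 166.41. The stated 166 reproduces and is then rounded up to 200. This is a precision formula for a single proportion. It gives no power for a two-arm VAS comparison, and the plan states no power.

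**3. Inputs for the gain.**
- From section 5c: N = 200, a standardised effect of 0.5, significance at 0.05, and a VAS SD of 1.1 (from a cited knee arthroplasty study, on movement at 24 h).
- Assumed: 100 per arm, two-sided test, no dropout, no Holm penalty, normal approximation.
- Assumed, because the documents give no value: the correlation r between preoperative and postoperative VAS, taken as 0.2, 0.3 and 0.5.

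**4. Formulas.**
- Cut in residual variance = r²
- Equivalent total N = 200/(1−r²)
- CI narrowing = 1 − √(1−r²)
- 95% CI half-width = 1.96 × 1.1 × √(2/100) × √(1−r²)
- Power: two-sample comparison with the residual SD multiplied by √(1−r²)

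| r | Variance cut | Equivalent N | CI narrower by | Half-width (VAS points) | Power, effect 0.5 | Power, effect 0.3 |
|---|---|---|---|---|---|---|
| 0 (no adjustment) | 0 | 200 | 0 | 0.305 | 94.2% | 56.4% |
| 0.2 | 4% | 208 | 2.0% | 0.299 | 95.0% | 58.1% |
| 0.3 | 9% | 220 | 4.6% | 0.291 | 96.0% | 60.4% |
| 0.5 | 25% | 267 | 13.4% | 0.264 | 98.3% | 68.8% |

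The effect of 0.3 is an assumption, included to show a case where power is not already high. For the planned Mann-Whitney test at an effect of 0.5, power is about 93.3% (relative efficiency 3/π under normality).

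**5. Which form of adjustment.** With equal SDs, a change score has variance 2(1−r) relative to the raw score: 1.6 at r = 0.2, 1.4 at r = 0.3 and 1.0 at r = 0.5. Below r = 0.5 it is worse than no adjustment, so the gain depends on using the baseline as a covariate.

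**The case against.** The strongest case against is that this is optional. On the plan's own effect of 0.5 the VAS comparison already has about 93–94% power. At r = 0.3 the CI half-width falls by only 0.014 points (0.305 to 0.291). The value of r is assumed. Section 5b excludes chronic pain and pain medication, which may narrow the baseline range. Pain at a clinic visit is also a different state from pain after surgery under a block or infiltration and an adductor canal catheter. The stated question is superiority between arms, not change from baseline, and the sole endpoint in section 5e is opioid consumption. Most of this stands, and it limits the size of the point.

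It does not remove the point. The power figure depends on an effect the protocol only expects, and it ignores the planned Holm correction. Showing baseline pain by arm is useful whatever r is, since chronic pain is an undefined exclusion in a knee arthroplasty population.

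A reader might infer stronger claims that the documents do not support:
- **That no preoperative pain score is recorded.** The undated item in section 5h neither schedules one nor rules one out.
- **That the VAS outcomes have to be compared raw.** Age, gender, ASA class and type of surgery are collected and could serve as covariates. The comparison is raw because section 5c chooses an unadjusted test. What is unavailable is adjustment for baseline pain.
- **That collecting the score would by itself tighten the comparison.** Under the planned Mann-Whitney test it adds no precision. The analysis must change too.

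**Conclusion.** The point holds as a low-cost improvement that should be made, not as an error in the plan. No preoperative VAS is specified, the one undated pain item does not supply it, and the planned analysis would not use it.

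A reader might take the missing baseline to mean a biased comparison. It does not: allocation is randomised, and the test's error rate already allows for chance imbalance. The loss is some precision on the VAS outcomes and one row of the baseline table. The documents show no benefit for opioid consumption.

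The likely size is modest: CIs about 2% to 5% narrower at r = 0.2 to 0.3, worth roughly 8 to 20 extra patients on 200. The larger figure of 13%, or about 67 patients, needs r = 0.5, which is less likely given the exclusions. All of these figures rest on the assumed r and on a pre-specified baseline-adjusted analysis.

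**What to change.** 1. In section 5h, give the time points of the undated pain item. State whether the trial's VAS scores are taken at rest or on movement; the plan does not say.
2. Add one VAS under that same condition at the existing preoperative clinic visit, before allocation, with a column in the data file. If a preoperative score is already intended, say so.
3. Show it by arm in the baseline table.
4. In section 5c, pre-specify a baseline-adjusted analysis of the VAS outcomes, by ANCOVA or rank ANCOVA with the preoperative score as covariate, in place of or alongside the Mann-Whitney test. If both are kept, say which one governs. Keep Bonferroni-Holm. Do not use change scores.
5. State how missing baseline values are handled, so that no randomised patient drops out of the VAS analysis for lack of one.

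Cost: one question per patient at a visit that already happens, one spreadsheet column, a few missing values, and a changed VAS analysis. That last item is more than an added term, since the plan has no regression model at present. No extra staff, visit or procedure is needed, and the opioid analysis is unaffected. Step 2 has to happen before a patient's surgery. Steps 3 and 4 can use only what has been collected by then.
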